### 2.3.2 Exclusion criteria

- $<18$  years of age
- Failure to provide informed consent to be followed up by study staff after release

## 2.4 Sampling scheme

### 2.4.1 Participant recruitment and informed consent

In liaison with DCS health staff, study staff will develop a line list of offenders on ART which will be updated regularly to identify potentially eligible and newly enrolled offenders initiated on ART. Individuals referred by DCS staff to the study team will be provided a brief description of the study in the correctional facility clinic. For those still interested in learning more, the study team member will proceed with the informed consent process including describing inclusion and exclusion criteria; post-release follow-up procedures including telephonic or home contact, clinical record review, and blood draw for viral load ascertainment at 6 months; the two study arms; and the randomization procedure. Consecutive offenders from the study sites who meet inclusion criteria and agree to be part of the study will be asked to provide written informed consent. Within the correctional facility, all the offenders who meet the inclusion criteria will be

invited to participate (Appendix A: EL001 Screening, eligibility and Enrolment). This process will take place between 1 week and 3 months prior to release.

#### 2.4.2 Randomization

We will perform individual randomization blocked by correctional facility. Study staff will open numbered envelopes with the allocation following enrollment. Participants will be randomized 1:2 to either the standard of care or the TCAC using sequential envelopes with study arm determination sealed inside (blocked by study site and based on random number generation). Participants and members of the research team recruiting and implementing the strategy will be unmasked to randomization assignment due to the behavioral nature of the strategy and need for team members to explain the study arm procedures to participants. Study assignments will be masked to staff performing outcome assessments and the investigators until all outcome data have been collected.

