## 2.7.2 Ascertainment of linkage to care

Study staff will contact participants to ascertain care status and update contact information at 30, 90 and 182 days from release. Follow up will primarily be telephonic and will rely on participant self-report. The scheduled visit windows are: Day 30 (from 20-70 days), Day 90 (from 71-150 days), and Day 182 (from 151 – 245). The last contact attempt will be made on Day 246. At the Day 182 visit, participants will be asked for in-person contact that will occur either at research offices or at a site convenient to the participant. This study visit will be used to ascertain visit status, socio-demographic data, and to complete surveys on stigma, social capital, and care satisfaction. In addition, a whole blood sample (8mL) will be obtained for HIV RNA quantification (viral load) if there are no clinic obtained HIV RNA results from within 60 days or 182 days post-release. Refer to schedule of CRFs for data collection tools used at each study visit.

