## 2.7.4 Viral loads at 6 months

Participants in the TCAC arm will have 6 month viral loads obtained at the TCAC. Participants in the care as usual (CAU) arm will have a specimen (2mL) drawn at 6 months for viral load assessment.

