## 2.8 TCAC post-release procedures

### 2.8.1 TCAC post release contact

Post-release, a study team member will make contact with the participant within 1 week to update contact details and to review attendance at TCAC sessions.

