## 2.9.2 Effectiveness of TCACs

**Primary outcome:** The primary outcome of this assessment is the proportion of participants with self-reported care at 6 months either in TCAC or DoH clinical care. Self-reported care at 6 months will be defined as – having at least two post-release HIV care visits 90 days apart with the last visit between 5 and 7 months from release. We will perform an analysis of retention in care at 6 months among all randomized individuals as an intent to treat analysis.

We will also perform an eligible for 6 month follow-up analysis. This analysis will exclude:

- Not released within 3 months of enrollment
- Re-incarcerated within 6 months of release
- Died within 6 months of release
- Withdrawn participation within 6 months of release

**Secondary outcomes:** We will also evaluate the effectiveness of TCACs compared to care-as-usual for the following secondary outcomes:

1. Verified in care at six months
2. Time to linkage to care
3. Linkage to care within 90 days of corrections release
4. HIV RNA <400 c/mL at 6 months - Viral load data at 6 months will be based on routinely collected viral load data (clinic records and the electronic National Health Laboratory System to determine 6 month viral load outcomes, successfully applied in prior studies) augmented by viral loads obtained by the study when 6 month viral load data are not available.
5. Social capital score change
6. Stigma index score change
7. Employment or self-employment

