### 5.1 Data collection tools

**Table 5: List of data collection tools and intended use**

Name of tool	Purpose	Schedule	Study arm
Visit Contact Documentation (AD001)	To collect and track information on all study contacts made with the participant during scheduled visit windows.	Pre-release Post-release	CAU TCAC
Pre-release locator Form (AD002)	To collect the participant's personal information important for identifying and contacting the participant for follow up after release.	Pre-release	CAU TCAC
Release Verification (AD003)	To verify participant release from the correctional facility and collect information of the documented date of release.	Post-release	CAU TCAC
Post-release locator Form (AD004)	To collect the participant's personal information important for identifying and contacting the participant for follow up after release.	Pre-release	CAU TCAC
Off Study (AD005)	To document discontinued participation in the study due to withdrawal, loss to follow up or end of the study procedures.	Pre-release Post-release	CAU TCAC
Screening, Eligibility & Enrolment (EL001)	To collect screen participant for eligibility, and collect enrolment information.	Pre-release	CAU TCAC

Baseline Demographics (DM001)	To collect participant demographic information at the time of enrolment	Pre-release	CAU TCAC
Demographics Follow-Up (DM002)	To update participant demographic information (where necessary) after correctional facility release.	Post-release	CAU TCAC
Pre-release Assessment (RK001)	To collect information on health and ART history, ASSIST substance use (alcohol and other drugs) screen, PHQ-9 depression screen, social capital, and stigma screens)	Pre-release	CAU TCAC
Post-release Assessment (RK002)	To collect information on health and ART history, ASSIST substance use (alcohol and other drugs) screen, PHQ-9 depression screen, social capital, and stigma screens)	Post-release	CAU - Day 30 visit TCAC- at first session
Routine Health Screening (RK003)	To closely monitor participant health status in order to guide referrals and session services following established study algorithms (includes symptom screen, and weight measurements).	Post-release	TCAC
Health Seeking (SS001)	To collect information on self-reported visits to access medical or non-medical HIV care and treatment services at any time after correctional centre release.	Post-release	CAU TCAC
Clinic Visit (SS002)	To collect details of self-reported participant clinic visits.	Post-release	CAU TCAC

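### Section 2.4.2 says outcome assessors are masked, but the plan's own procedures cannot assure this for the self-reported primary outcome

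*Combined protocol and SAP*

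**What the plan says.** Section 2.4.2 divides people into two groups. On one side, "Participants and members of the research team recruiting and implementing the strategy will be unmasked to randomization assignment", because the strategy is behavioural and has to be explained. On the other, "Study assignments will be masked to staff performing outcome assessments and the investigators until all outcome data have been collected". No section says who the assessors are, how they are kept apart from other study staff, or how they are shielded from the allocation.

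The primary effectiveness outcome (Section 2.9.2) is "the proportion of participants with self-reported care at 6 months either in TCAC or DoH clinical care". It requires two post-release HIV care visits 90 days apart, the later one 5 to 7 months after release. Section 2.7.2 says how status is obtained: "Follow up will primarily be telephonic and will rely on participant self-report". Table 5 lists form SS002 for both arms, with the purpose "To collect details of self-reported participant clinic visits".

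Two further steps depend on the arm. Table 5 schedules RK002 at the Day 30 visit for care as usual and at the first TCAC session for the other arm. Section 6.3, item 7, offers extra counselling to non-intervention participants who have not entered community care within 90 days.

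**The concern.** The masking statement covers all outcome assessment, yet the primary outcome is a conversation between study staff and a person who knows the allocation, about visits that may have taken place at the intervention itself. Once a TCAC visit is mentioned, the interviewer knows the arm.

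This matters because classification depends on dates. Whether someone meets the two-visit rule can turn on how hard the interviewer presses for a second date or for a visit inside the 5 to 7 month window. If that effort differs by arm, the difference enters the comparison directly. Section 5.3.5 acknowledges that participants may give socially acceptable answers but does not mention interviewers knowing the arm. A reader of Section 2.4.2 would therefore credit the primary result with a protection that has not been put in place.

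**Working it through.** **1. Statement against procedure**

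| Element | Section | Consequence for masking |
|---|---|---|
| Assessors masked until all outcome data are in | 2.4.2 | Claim; no mechanism given |
| Participants unmasked | 2.4.2 | Can disclose the arm at any contact |
| TCAC visits count towards the primary outcome | 2.9.2 | A reported TCAC visit identifies the arm |
| Status by self-report to study staff, mainly by telephone | 2.7.2 | The person recording the outcome hears the disclosure |
| First visit to a clinic or to a TCAC told apart in the TCAC arm | Table 2 | Place of first visit has to be known from some source |
| RK002 at Day 30 in one arm, first session in the other | Table 5 | Whoever runs Day 30 must know whether RK002 is due (Table 7 does not list it) |
| 90-day counselling for one arm only | 6.3, item 7 | Whoever acts on 90-day status must know the arm |

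The documents do not separate the staff in the last two rows from those who record the primary outcome.

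**2. How many participants could disclose the arm through a TCAC visit**

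Section 4.1 assumes that 40% to 66% of the 120 TCAC-arm participants transition to a TCAC: 120 × 0.40 = 48 and 120 × 0.66 = 79. These 48 to 79 people can identify themselves by naming where they were seen. The other 41 to 72 in that arm, and the 60 in care as usual, need not be identified by this route. Disclosure is therefore partial, and it falls in one arm only.

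**3. The plan's own power figure**

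This sets the scale for step 4. Inputs from Section 4.1: 60 and 120 participants, 78% ascertainment, 0.25 versus 0.49, alpha 0.05 (taken as two-sided).

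- Effective sizes: 60 × 0.78 = 46.8 and 120 × 0.78 = 93.6.
- Pooled proportion: (46.8 × 0.25 + 93.6 × 0.49) / 140.4 = 0.41.
- SE0 = √[0.41 × 0.59 × (1/46.8 + 1/93.6)] = 0.0881.
- SE1 = √[0.25 × 0.75/46.8 + 0.49 × 0.51/93.6] = 0.0817.
- Power = Φ[(0.24 − 1.96 × 0.0881)/0.0817] = Φ(0.825) = 79.5%.

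The stated 80% is reproduced.

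**4. Illustration of differential over-reporting**

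Assume no true effect, a true in-care proportion p in both arms, and a proportion f of TCAC-arm participants not in care who are wrongly recorded as in care, with no such error in care as usual. The spurious difference is d = (1 − p) × f. The false-positive rate is Φ[(d − 1.96·SE0)/SE1] + Φ[(−d − 1.96·SE0)/SE1], with SE0 and SE1 recalculated at p and p + d for the sizes in step 3.

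The values of f are assumptions. The value p = 0.44 borrows the prior 6-month ART continuity in Section 1.1; p = 0.25 is the Section 4.1 example.

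| f | d at p = 0.44 | False positive | d at p = 0.25 | False positive |
|---|---|---|---|---|
| 0.05 | 0.028 | 6.1% | 0.0375 | 7.2% |
| 0.10 | 0.056 | 9.5% | 0.075 | 14.2% |
| 0.15 | 0.084 | 15.4% | 0.1125 | 26.0% |
| 0.20 | 0.112 | 23.9% | 0.150 | 41.5% |

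The table shows how sensitive the comparison is to differential error from any source. It does not isolate the interviewer's share. People not in care have no true TCAC visit to disclose, so most of f would be participant over-reporting.

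**The case against.** Several points on the other side stand.

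- **Viral load.** A reader might point to "Participants in the TCAC arm will have 6 month viral loads obtained at the TCAC" as proof of unmasked measurement. HIV RNA is a laboratory value, and Section 2.9.2 draws on routine results first. The place of the draw may affect completeness, but hardly the result.
- **Early TCAC contact.** Section 2.8.1 says "a study team member will make contact with the participant within 1 week to update contact details and to review attendance at TCAC sessions". This is delivery of the strategy by people Section 2.4.2 already calls unmasked; it is not outcome assessment.
- **Day 182 surveys.** Section 2.7.2 places these at research offices or another convenient site. They are not described as held at the TCAC.
- **Existing safeguards.** The outcome is already a date rule, TCAC attendance is logged electronically (Section 2.8.2), and record-verified care at six months is a planned secondary outcome.
- **Stakes.** Section 4.1 presents power as illustration only, and Section 6.7 has no stopping for effectiveness.

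Two points stand in part. The wording of SS001 and SS002 is not in the documents, so a protective script cannot be ruled out; but the outcome definition counts TCAC visits, and an unmasked participant may name the place unprompted. Section 6.3 also describes a before-and-after design that does not fit this randomised trial, so its counselling offer may not be meant to apply here. If so, that strand drops out, and the argument from the primary outcome is unaffected.

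The pilot status lowers the stakes but does not remove the point: effectiveness on self-reported care is a listed primary objective, and the pilot is meant to yield the protocol for a full trial.

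**Conclusion.** The concern holds in a limited form. Assessor masking is stated without a mechanism, and for the self-reported primary outcome the plan's procedures do not deliver it reliably. On the plan's own transition assumption, 48 to 79 of the 120 TCAC-arm participants could disclose their arm by naming a TCAC visit.

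Two stronger conclusions are tempting, and the documents support neither. One is that the trial has no masking at all. Nothing shows that the investigators are unmasked, and laboratory viral loads and record verification do not depend on what an interviewer is told. The other is that 2.8 to 11.2 points measures assessor bias. Those figures rest on assumed error rates and largely describe participant over-reporting, which would remain with perfectly masked interviewers. Nor should 0.112 be read as nearly half of the planned 0.24: the first uses a base rate of 0.44 for ART continuity, the second a base rate of 0.25 for care with an undetectable viral load. The size of any interviewer effect cannot be derived from the documents.

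**What to change.** 1. Amend Section 2.4.2 to say that masking of interviewers cannot be assured for the self-reported outcome. Limit the masking claim to investigators and to laboratory or record-based outcomes.
2. At the Day 182 contact, record all HIV care visit dates before asking where care was received, and derive in-care status by program from the dates. This reduces the room for differential probing but does not restore masking: an interviewer may have learned the arm at the Day 30 or Day 90 contact, or the participant may volunteer it. That is why the first change is still needed.
3. Whenever the self-reported primary result is presented, show the already planned record-verified result beside it, with a table of agreement between the two by arm. The table would also reveal over-reporting by participants that differs by arm, as far as records can be found.

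The cost is a wording change, a new question order on existing forms and one cross-tabulation. No extra staff, visits or participants are needed. The downside is that the stated design looks slightly less rigorous.

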### 2.5 Pre-release study procedures

All participants will have a baseline demographic, health, and incarceration history questionnaire. In addition the ASSIST substance use tool, social capital questionnaire, and stigma index will be used with all participants. Participants will have a second pre-release contact with study staff if release is more than one week from enrollment. The purpose of this visit will be to review the study, the allocation arm, and to encourage linking to care following release.

#### 2.5.1 Care-as-usual (CAU) study arm

Participants will have a pre-release session with a study team member. The goal of the session is to review study procedures, review contact from the study team or contacting the study team following release, update any changes in contact information, and to encourage post-release linkage to care. This session will occur 1 – 2 weeks prior to release. Per DCS routine, at release, participants will receive a referral letter from the DCS health services and will be dispensed ART (the duration ranges from 30-90 days and is determined by the DCS staff) prior to release.

#### 2.5.2 TCAC study arm

Participants will have a pre-release session with a study team member. The goal of the session is to review contact from the study team or contacting the study team following release, update any changes in contact information, and to encourage post-release linkage to care. In addition, participants will be reminded of the location and timing of the TCAC session that they have been assigned to and will be provided a contact number for a TCAC facilitator. At release the TCAC arm will also receive a referral letter describing ART regimen and a supply of ART (per DCS routine).

## 2.6 Verification of release

Study staff will work with DCS health and security officials to, (1) verify whether participants have been released based on the release dates provided at study enrollment, and (2) identify inmates released without study staff knowledge.

## 2.7 Post release follow-up

The tracing of participants will primarily be based on the tracing plan developed with the participant during the in-correctional facility contact sessions (Appendix A: AD001 Locator and Tracing Plan). The tracing plan will contain information on alternative addresses at which the participant anticipates staying after release, if they plan to be at the same address in 3 months and 6 months, names and contacts of next of kin (part of informed consent), telephone numbers, and study staff contact information. After the participant has been released, study staff will also liaise with Community Corrections Department (CCD) staff to obtain extra information on where the participant is actually released to. The following strategies for tracing will be performed:

- Participants will be educated to telephonically contact a study team member within 15 days of release; for which they will receive a small incentive in the range of a ZAR 20 - 50 (US\$3-7) airtime vouchers. Offenders will be instructed to send “call-me” messages to an allocated study cell-phone number that the case manager can access and respond to, thereby making the calls free for the ex-offenders.
- In the event that participants fail to initiate contact, study staff will use available contact information from the tracing plan or CCD staff to contact released offenders at the determined follow-up time points.
- If no contact is made via participant or study staff initiation, the case worker will work with CCD staff (who have contact details for all paroled individuals) to contact the released offender.

### 2.7.1 First post-release contact

The first contact with participants post-release will be conducted during 1-15 days after the participant’s release. The purpose of this visit is to verify if the participant’s contact details provided are still applicable and to find out the geographical area where the participant was released and remind the participant of study procedures. All participants will be reminded about the importance of linking into care. Following the first contact standard “*hello, are you well?*” messages will be sent every 2 weeks to maintain connection with the participant.

## 2.7.2 Ascertainment of linkage to care

Study staff will contact participants to ascertain care status and update contact information at 30, 90 and 182 days from release. Follow up will primarily be telephonic and will rely on participant self-report. The scheduled visit windows are: Day 30 (from 20-70 days), Day 90 (from 71-150 days), and Day 182 (from 151 – 245). The last contact attempt will be made on Day 246. At the Day 182 visit, participants will be asked for in-person contact that will occur either at research offices or at a site convenient to the participant. This study visit will be used to ascertain visit status, socio-demographic data, and to complete surveys on stigma, social capital, and care satisfaction. In addition, a whole blood sample (8mL) will be obtained for HIV RNA quantification (viral load) if there are no clinic obtained HIV RNA results from within 60 days or 182 days post-release. Refer to schedule of CRFs for data collection tools used at each study visit.

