**Barriers to the transition from corrections to community care:** Post-release, ex-inmates are expected to use the referral letter to establish care with Department of Health (DoH) clinics. It is the responsibility of the ex-inmate to identify the clinic and the appropriate days to go, and to advocate for his or her care. There is no active follow-up provided by DCS or DoH to confirm a successful transition, nor is there specific coordination between the DCS and the DoH regarding the release of ex-inmates receiving HIV care. Because of the absence of formal communication between the DCS and the DoH there is no documentation of the transition of care from corrections to community care to inform patient care, care continuum indicators, or quality improvement. The impressive HIV care outcomes observed in correctional settings in South Africa drop off dramatically following release from corrections. Ex-inmates living with HIV encounter unique care transition challenges across the socio-ecological framework. Qualitative and quantitative research conducted by the PI ([name]) and co-I ([name]) with 492 ex-inmates in South Africa, identified several important themes related to the transition in care among ex-inmates. These include the clinic experience, social capital, stigma, substance use (11% of participants with identified drug use), re-incarceration, and economic insecurity. Depression also affects the transition from corrections to community care in the United States, but has not been evaluated in this context in South Africa. Substance use is another barrier to the care transition. Substance use itself interferes with care seeking due to increased impulsivity as well as diminished social capital. As a result of these barriers, at 6-months following release, only 44% had continuity in antiretroviral therapy ([name] unpublished data).

**Barriers to care engagement in the general population in Africa:** Experience with the general population living with HIV provides additional insight regarding potential barriers for ex-inmates. On the individual level of the socio-ecological model, knowledge of HIV, self-efficacy, fatalism,

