#### **2.8.9 Schedule of TCAC medical evaluations**

In addition to the standard structured group activities, there is a list of individual activities focused on health assessment and ART management and based on duration from release. These components are as follows:

1. **First session:** Health and ART history review, ASSIST substance use (alcohol and other drugs) screen, PHQ-9 depression screen, social capital, and stigma screens. The results of these tools will be used for guiding referrals and session services. This screening will occur on arrival at the TCAC session.
2. **Every session:** At every session the following will be performed: symptom screen, weight measurement. An algorithm for action or non-action will be developed. Based on the

algorithm, study staff may collect sputum, or refer participants to a primary care clinic based on the symptom screen and weight.

3. **At 6 months:** Laboratory assessment with HIV RNA, creatinine, and CD4 count. In addition, starting at 6 months, participants will be evaluated for transition to standard services including community adherence club, community chronic medication distribution, or clinic medication fast lanes.

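### The rule for the 6-month viral load is inconsistent across sections and, read literally, lets an early post-release result stand in for the 6-month value

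*Combined protocol and SAP*

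**What the plan says.** Section 2.7.2 asks every participant for an in-person contact at Day 182 (window Days 151-245). There, an 8 mL sample is taken for HIV RNA only "if there are no clinic obtained HIV RNA results from within 60 days or 182 days post-release". The sentence is not limited to one arm.

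Section 2.7.4 splits the rule by arm and attaches no condition about clinic results. For the intervention arm, "Participants in the TCAC arm will have 6 month viral loads obtained at the TCAC". For the control arm, "Participants in the care as usual (CAU) arm will have a specimen (2mL) drawn at 6 months for viral load assessment". Section 2.8.9 supports the first of these by listing, at 6 months in the TCAC, "Laboratory assessment with HIV RNA, creatinine, and CD4 count".

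Section 2.9.2, secondary outcome 4, sets an order of sources: "Viral load data at 6 months will be based on routinely collected viral load data", "augmented by viral loads obtained by the study when 6 month viral load data are not available". It gives no days that count as 6 months.

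The result is used in two places. Table 3 compares HIV RNA below 400 c/mL by arm among those in care, with a chi-square test. Sections 2.9.1 and 4.2.1 set a feasibility target of viral-load ascertainment in at least 95% of participants in care.

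**The concern.** Staff at the Day 182 visit will use the sentence in 2.7.2 to decide whether to take blood. A specimen not taken then cannot be recovered, so the wording is operative, not background.

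A result from soon after release largely reflects treatment received in corrections. Section 1.1 says of that period: "The impressive HIV care outcomes observed in correctional settings in South Africa drop off dramatically following release from corrections". If such results stand in for the 6-month value, the outcome no longer measures what its name says. If they do so more often in one arm, the comparison is affected as well.

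The rule also bears on primary objective 1, which includes feasibility of endpoint ascertainment: whether a Day 40 result counts as ascertained changes the numerator of the 95% target. Section 1.2 names being in care with an undetectable viral load at six months as the primary outcome of the later full trial, and section 4.1 describes this pilot's primary outcome in the same terms. The pilot is meant to leave a protocol ready for that trial.

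**Working it through.** **The plan's own figure.** The only computed figure that involves viral load is the power statement in section 4.1: 80% for 0.25 versus 0.49, with 60 and 120 participants and 78% ascertained. It reproduces:
- n = 60 × 0.78 = 46.8 and 120 × 0.78 = 93.6
- pooled proportion = (46.8 × 0.25 + 93.6 × 0.49) / 140.4 = 0.41
- null SE = √[0.41 × 0.59 × (1/46.8 + 1/93.6)] = 0.0880
- alternative SE = √[0.25 × 0.75/46.8 + 0.49 × 0.51/93.6] = 0.0817
- power = Φ[(0.24 − 1.96 × 0.0880)/0.0817] = 0.795 (two-sided alpha assumed)

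Nothing below depends on it.

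**The rules side by side.**

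| Section | Arm | When the study or TCAC draws | Days that count | Volume |
|---|---|---|---|---|
| 2.7.2 | both | only if no qualifying clinic result | 60 days 'or' 182 days | 8 mL |
| 2.7.4 | TCAC | always, at the TCAC | 6 months, no window | not given |
| 2.7.4 | CAU | always | 6 months, no window | 2 mL |
| 2.9.2 | both | only if no 6-month routine result | 6 months, no window | not given |

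Sections 2.7.2 and 2.9.2 agree on the order of sources (routine first, study draw as back-up) but not on timing. Section 2.7.4 differs from both because it is unconditional. No section ranks them or says which of several results to use. Section 2.7.2 points to the schedule of case report forms, but Tables 6 to 8 do not list the laboratory form LT001, so the schedule does not settle it.

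**Day arithmetic.**
- Literal reading: a result from Days 0-60 waives the draw. The latest such day is 151 − 60 = 91 days before the visit window opens and 182 − 60 = 122 days before Day 182. If the second limb also means 'within', any day up to 182 qualifies.
- 'Of' reading: 182 − 60 = 122 and 182 + 60 = 242, so Days 122-242. This still opens 151 − 122 = 29 days before the visit window, and it closes 245 − 242 = 3 days before the visit window does.

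**Where the arms could diverge.**
- 2.7.4 applied to both arms: both are measured at about 6 months.
- 2.7.2 with 2.9.2 applied to both arms: the timing rule is the same in both.
- 2.7.2 and 2.9.2 applied to CAU, with 2.7.4 and 2.8.9 applied to TCAC attendees: CAU results carry routine dates and TCAC results carry the month-6 session date. Only this mix gives arm-specific timing.

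**Size.** If a share f of CAU results is early, and early suppression exceeds 6-month suppression by d points, CAU suppression is overstated by f × d. The documents give neither f nor d. Purely as an assumption, d of 10 to 20 points gives 1-2 points at f = 10%, 2.5-5 at f = 25% and 5-10 at f = 50%. These values show how the formula scales; they are not an estimate.

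**The case against.** The literal reading is nearly incoherent. If any result within 182 days qualified, the 60-day limb would add nothing. Reading 'or' as 'of' makes sense of the sentence and fits the 6-month wording in 2.4.1, 2.7.4 and 2.9.2. This stands as the probable intent. It removes the very early results but leaves the conflict with 2.7.4, the missing selection rule and a window that does not match the visit window.

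A reader might infer that the plan does inflate CAU suppression and hide a TCAC benefit. The documents do not support that. No section prescribes the mix of rules that would produce it, and 2.7.4 itself gives CAU a specimen at 6 months. Table 3 restricts the comparison to those in care, so a general drop-off after release does not translate directly into lower suppression in that group. Participants also leave with a supply of ART (30 to 90 days in 2.5.1), so many may have no clinic contact in the first weeks.

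A reader might also infer that TCAC-arm participants who stop attending have no planned draw. That holds only if 2.7.4 is read alone. Sections 2.7.2 and 2.9.2 provide a back-up draw without regard to arm, and Table 5 lists LT001 for both arms. Which section governs still matters: section 4.1 assumes 40 to 66% transition to TCACs, so 120 × 0.34 ≈ 41 to 120 × 0.60 = 72 people in that arm may not be attending.

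Finally, HIV RNA below 400 c/mL is listed as a secondary outcome, in a pilot that section 4.1 says is not an effectiveness study. That limits the consequence for this trial's conclusions.

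**Conclusion.** The point holds as a contradictory, and literally wrong, measurement rule for the HIV RNA outcome and for the 95% ascertainment target. That rests on the text alone. Different timing by arm is a possibility that depends on how staff combine the sections. Overstated CAU suppression is the likely direction if that happens, but its size cannot be computed from the documents and no percentage-point figure should be attached to it. If 'of' was intended, the timing problem shrinks to results from Days 122-150, and the inconsistency between sections remains. It should be corrected before follow-up visits begin, because missed specimens cannot be replaced.

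**What to change.** State one rule for both arms and use it in 2.7.2, 2.7.4 and 2.9.2:
- The 6-month viral load is the result nearest Day 182 whose specimen date falls inside one stated window, from any source (clinic, laboratory system, TCAC or study).
- The window must contain the Day 182 visit window. Days 151-245 does so; Days 122-245 does so if the 60-day intent is kept. Days 122-242 does not, since a valid study draw on Days 243-245 would fall outside it.
- If there is no such result, the study draws a specimen at the Day 182 visit, regardless of arm or TCAC attendance.
- Count a viral load as ascertained for the 95% target only if it meets this rule.

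In the same edit, reconcile the 8 mL and 2 mL statements and add LT001 to the schedule of forms.

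The cost is one paragraph and possibly a few more Day 182 draws than under the literal 2.7.2 rule; 2.7.2 and 2.7.4 already provide for such draws. The narrower window limits timing differences between arms but calls for more draws; the wider one does the reverse.
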